Analysis: Descriptive statistics surrounding the ease of use on a 5-point likert (very easy to very difficult) will be analyzed on five different aspects of use. Specifically, the steps of using the Mosie Kit (collecting a sperm sample, drawing up the sample in the Mosie syringe, inserting the syringe, and depositing the sperm at or near the cervix) and overall ease of use will be examined. Additionally questions related to use such as comfort, ease and safety of the process, enjoyable and intuitiveness of use (able to use it without instructions) will allow the user to rate their experience from Strongly agree to strongly disagree (5 point scale). The data will be plotted and examined as part of the analysis.

Secondary Hypothesis 2: The participants were able to use the Mosie Kit as instructed using the instructions contained in the kit. The alternative hypothesis is that the participants were not able to use the kit using the instructions contained in the kit.

Analysis: Descriptive analysis of perceived overall success rate will be analyzed. Additionally, descriptive analysis of the frequency of each expected behavior related to use of the kit will be examined.

Secondary Hypothesis 3: The participants reported they used the kit as intended, specifically, using it within 24 hours of initial signs of ovulation and again 24-48 hours after ovulation was confirmed or expected. The alternative hypothesis is that the participants report they did not use the kit as intended with respect to timing (within 24 hours of initial signs of ovulation and again 24-48 hours post ovulation).

Analysis: Frequency rates related to timing of insemination at all reported cycles will be analyzed. The data will be reported in both total number of attempts at each time point as well as percentage of attempts at each time point in comparison with total cycles where the Mosie Kit was used. T-tests will also be used in this analysis. Additionally,

amount of time lying after insemination and position of lying will be analysed using descriptive statistics and correlations with pregnancy rate.

Secondary Hypothesis 4: Participants reported they perceived the Mosie Kit to be a safe way to conceive. The alternative hypothesis is that participants did not perceive the Mosie Kit to be a safe way to conceive.

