9.2 Sample Size Determination

The desired final sample size for this study is 500 completed surveys. This will produce a 95% confidence interval with +/- 4.4% within larger populations. In order to obtain that rate of respondents, the study will invite about 50% people who have ordered a Mosie Kit in the prior 2-8 months to the study start date. It is expected that approximately 4000 people will be invited to participate. By inviting 4000 potential participants, it is expected that with a response rate of 15% approximately 600 will complete the survey. Currently Mosie has about a 20% open rate on their general emails. For this reason, all people who purchased a kit within the last 2-8 months will be invited to participate.

According to the sample size tables, a response rate of 384 is sufficient to provide a 95% confidence interval with a 5% margin of error rate. While the total number of respondents can not be controlled, every effort will be made via the reminder emails to obtain at least 500 participants but no less than 384.

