9.4 Statistical Analyses

9.4.1 General Approach

Statistical analysis will commence with descriptive statistics for each survey question and plotting of the individual data into scatter plots to understand the data distribution. If any information suggests corrective procedures should be employed, the appropriate transformation or non-parametric test will be used.

Categorical values will be reported using descriptive statistics and frequency of occurrence. Key categorical values will also be converted into a percentage of total responses in order to allow an understanding of the prevalence of the response in the sample. For continuous variables, the means with standard deviations, median and range will be reported.

Qualitative data is only expected as a response to two questions, an open ended safety question and an additional comments question. The responses will be evaluated and categorized. Then the frequency of each category will be provided.

For inferential tests such as t-tests and ANOVAs, a p-value of 0.05 and a confidence interval of 95% will be used for statistical significance. The type of hypothesis will determine whether the specific tests will be one-tailed or two-tailed. Hypothesis seeking to understand whether there is or is not a difference will use a two-tailed test while those seeking a greater than or less than relationship will use a one-tailed test. Correlations among some of the variables will also be examined as appropriate.

Statistical analysis process for each hypothesis has already been described in section 9.1. No baseline analysis is used for cross-sectional studies. No interim analyses are planned for cross-sectional one survey studies.

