9.4.3 Exploratory Analyses

Additional exploratory data analysis will be conducted to examine the main characteristics of the data. This analysis will be done using descriptive statistics, scatter plots, and odds ratio. If the exploratory analysis warrants the testing of new hypotheses, t-test or ANOVA may be used for further analysis.

Exploratory modeling will be conducted to examine multiple variables and their relationship to the pregnancy outcome. This will include the source of infertility, age, number of inseminations, number of cycles, lying time, and type of relationship. The model will use correlations and goodness of fit tests in its analysis.

1 0 SUPPORTING DOCUMENTATION AND OPERATIONAL CONSIDERATIONS

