[figure not shown]
How did you or your partner time your ovulation? (Select all that apply.) *
Count days in cycle
Track vaginal or cervical fluids
Tracking changes in the cervix
Use ovulation predictor kit
Use an app to estimate ovulation
Basal Body Temperature
Wearable device
Did not time ovulation
Did using Mosie result in a pregnancy? *
O Yes
O No
Back Next Page 10 of 20

[figure not shown]
Never submit passwords through Google Forms.

 $This \ content \ is \ neither \ created \ nor \ endorsed \ by \ Google. \ \underline{Report \ Abuse} - \underline{Terms \ of \ Service} - \underline{Privacy \ Policy}$

Google Forms

Page 56

[figure not shown]

Safe process

Enjoyable

	Very Easy	Easy	Neutral	Difficult	Very Difficult
To collect the semen/sperm sample in the cup?	0	0	0	0	0
To draw up the semen/sperm in the syringe?	0	0	0	0	0
Insert the Mosie syringe into the vagina up to the handles?	0	0	0	0	0
To deposit the semen/sperm at or near the cervix using the syringe?	0	0	0	0	0
My overall impression on the ease of use	0	0	0	0	0
					Page 12 of 20
submit passwords to	through Google Fo				

MOSIE-001 © 2020 Mosie Baby Page 59

MOSIE-001 © 2020 Mosie Baby

Page 60

Pulled the syringe plunger back and forth to confirm it was functioning.

My partner washed their hands

Use a sperm friendly-lubricant.

Thawed out donor sperm from sperm bank

Prepared all items and have them handy ready to use.

Washed the penis

that	apply)?*
	Lie down in a comfortable position.
	Relax
	Receive oral sex
	Stimulate clitoris
	Use any vibratory or non-vibratory stimulation device intravaginally
	Have an orgasm
	Other:
	erall, how well were you able to use the Mosie syringe to inseminate yourself our partner? * Very Able
	our partner? *
or y O O O	our partner? * Very Able Able Not Very Able
or y 0 0 0 0	Very Able Able Not Very Able Not Able at All Volume at All Volume at All Volume at All Volume at All Able at All Volume at All Able at All Able at All
or y O O O	Very Able Able Not Very Able Not Able at All Volong did you remain laying down after using the Mosie syringe? * Less than 15 minutes

Willelf best descri	ibes your lying position? *	
On my stomach	n	
On my side		
On my back		
On my back wit	th my hips elevated by a pillow	
Other:		
O No		
O		
What type of sam	ple did you use? *	
What type of sam	ople did you use? * rom a sperm bank (frozen)	
What type of sam	rom a sperm bank (frozen)	

0 2000	thank 50%	
O 51%-	70%	
O 71% -	80%	
O 81%-	90%	
O 90%-	95%	
O 96%-	100%	

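### Lying position has no natural order, so the planned correlation with pregnancy has an arbitrary sign and size and should be replaced by rates and a test for unordered categories

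*Combined protocol and SAP*

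**What the plan says.** Section 9.1, in the analysis paragraph for Secondary Hypothesis 3, plans that time lying down and "position of lying will be analysed using descriptive statistics and correlations with pregnancy rate". It names no coefficient, no numerical coding and no reference category.

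In Appendix A the position question offers stomach, side, back, back with hips elevated by a pillow, and other. Pregnancy is a yes/no item: "Did using Mosie result in a pregnancy".

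Section 9.4.1 adds general rules:
- On categorical answers: "Categorical values will be reported using descriptive statistics and frequency of occurrence".
- On the level of inferential tests: "a p-value of 0.05 and a confidence interval of 95% will be used for statistical significance".
- On sidedness, the choice between one and two tails is left to the type of hypothesis, and no direction is stated for lying position.
- A transformation or non-parametric test is allowed if the data suggest one, and correlations may be examined where appropriate.

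Section 9 names no chi-square test, exact test or logistic regression. Section 9.4.3 describes an exploratory model of pregnancy that includes source of infertility, relationship type and lying time, but not lying position. Of this model it says: "The model will use correlations and goodness of fit tests in its analysis".

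**The concern.** A correlation coefficient measures how far one variable rises or falls with another. That has meaning only if the categories can be ranked. Stomach, side, back, hips raised and other cannot be ranked, so whoever analyses the data must assign numbers, and the result inherits that choice. Reversing the numbers always reverses the sign. Re-ordering them changes the size and can move the result across the 0.05 line.

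Two readers of the same data could report opposite directions, or a real difference between positions could be missed because the chosen numbering does not line up with it. The non-parametric option in 9.4.1 does not help, because Spearman's coefficient also needs an order.

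**Working it through.** **The plan's own figure.** Section 9.2 states: "The desired final sample size for this study is 500 completed surveys", and "This will produce a 95% confidence interval with +/- 4.4% within larger populations". With half-width = 1.96 × √(0.25/n), n = 500 gives 4.38% and n = 384 gives 5.00%. Both stated figures reproduce. Neither concerns lying position.

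**Inputs.** From the documents: N = 500, five position answers, a yes/no outcome, alpha 0.05. Assumed: a two-sided test, and all counts and pregnancy rates by position, since the documents give none.

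**One table in full (Table 1).** Counts in survey order are 10, 60, 130, 270, 30. Pregnancies are 2, 12, 39, 97, 6 (20, 20, 30, 36, 20%), in total 156/500 = 0.312.

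*Test for unordered categories.* Chi-square = Σ nᵢ(pᵢ − p)² / [p(1 − p)]. The numerator is 0.125 + 0.753 + 0.019 + 0.603 + 0.376 = 1.876. The denominator is 0.312 × 0.688 = 0.2147. The result is 8.74 on 4 df, p = 0.068, whatever the numbering.

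*Correlation, codes 1 to 5 in survey order.*
- Mean code = 1750/500 = 3.5; variance = 6490/500 − 3.5² = 0.73.
- Covariance = 561/500 − 3.5 × 0.312 = 0.030.
- r = 0.030 / √(0.73 × 0.2147) = +0.076, p = 0.09.

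*All 5! = 120 numberings.* r runs from −0.129 to +0.129 (smallest p = 0.004). Twenty are significantly positive, 20 significantly negative and 80 not significant. The equal split is automatic, because each numbering has a mirror image.

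**Other assumed tables (N = 500, Pearson).**

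| Table | Counts | Rates (%) | Chi-square p | Survey-order r (p) | Numberings +/−/not significant |
|---|---|---|---|---|---|
| 2 | 100 each | 10, 20, 15, 25, 15 | 0.056 | +0.056 (0.21) | 16/16/88 |
| 3 | 20, 60, 160, 240, 20 | 10, 15, 15, 25, 15 | 0.065 | +0.100 (0.025) | 34/34/52 |
| 4 | 20, 60, 160, 240, 20 | 25, 10, 20, 15, 15 | 0.31 | −0.021 (0.63) | 3/3/114 |
| 5 | 10, 40, 150, 290, 10 | 10, 25, 14.7, 20, 20 | 0.48 | +0.024 (0.60) | 0/0/120 |

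Spearman gives the same picture (16/16/88 in Table 2, 36/36/48 in Table 3). If all positions have the same observed rate, r = 0 under every numbering.

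**How much of the difference the coefficient sees.** N × r² is the part of the chi-square that lies along the chosen numbering. In survey order this is:
- Table 1: 500 × 0.0758² = 2.87 of 8.74, or 33%.
- Table 2: 500 × 0.0565² = 1.59 of 9.21, or 17%.
- Table 3: 500 × 0.1004² = 5.04 of 8.83, or 57%.

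The share depends on the accident of the numbering. This is the sense in which power is misdirected.

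**Error rate with no true effect.** In simulated data with the Table 1 counts and 30% pregnancy in every position, survey-order coding fixed in advance is significant in about 5% of datasets, as is the chi-square test. Only a search over all 120 numberings for the best one gives about 33%.

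**The case against.** The strongest reply is that the plan never says it will put numbers on the answers. Correlation can be a loose word for association. Cramér's V, or a yes/no indicator for each position, would not depend on numbering. The same sentence also promises descriptive statistics, so any coefficient would sit beside a summary of the data. In Table 1 the survey-order result (p = 0.09) leads to the same conclusion as chi-square (p = 0.068). All this is fair. It limits the consequence but does not remove the fault: the ordinary meaning of correlation is a coefficient on numbers, the plan names no alternative, and Table 3 shows that survey order can disagree with chi-square (0.025 against 0.065).

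Three stronger readings are tempting, and the documents do not support them.

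- *A reader might infer that false positives rise to about a third.* That needs a search over numberings, which the plan does not propose. One numbering fixed in advance keeps about 5%.
- *A reader might infer that the 9.4.3 model is only a set of pairwise correlations with the same fault.* The section does not say pairwise. Its mention of goodness of fit implies a fitted model, and lying position is not in it. The infertility question asks about diagnoses or issues in the plural, which suggests that several may be ticked. Separate yes/no indicators would have no ordering problem.
- *A reader might infer that a spurious position effect will pass into user instructions.* Section 2.3.2 says that results may be used to improve the instructions, but it does not mention position; the use factor that it ties to pregnancy outcome is the timing of insemination.

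**Conclusion.** Wrong as written, with low impact. For lying position the planned correlation on numeric codes has an arbitrary sign and size, and it can miss or misstate a real difference between positions. The type I error of a single pre-fixed coding is not inflated.

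The size depends on the data. In the assumed tables, between none (Table 5) and 68 (Table 3) of the 120 numberings reach significance, and the sign reverses in all five. Whether significance changes depends on how far the observed rates differ. These figures rest on invented counts and rates, a two-sided 0.05 level and N = 500. The dependence on coding does not rest on them: it follows from the answers having no order.

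Position is an add-on under a secondary hypothesis about timing. It has no hypothesis or decision rule of its own, and no primary result or sample-size figure depends on it.

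**What to change.** In section 9.1, Secondary Hypothesis 3:
- For lying position, replace the correlation with the pregnancy rate in each position with its 95% confidence interval, and a two-sided 5x2 chi-square test, or an exact test where expected counts are small. In Table 1 the smallest expected count would be 10 × 0.312 = 3.1.
- State how free-text other answers are handled: recoded where possible, kept as a fifth group, or left out of the test.
- Keep a rank correlation or trend test for lying time only, whose answers are ordered bands.

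As a secondary point, in section 9.4.3 name the exploratory model as a logistic regression for pregnancy. Enter relationship type as a categorical term with a stated reference group, and each infertility source as its own yes/no indicator, since respondents may report more than one.

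The cost is a few lines of analysis text, settled before the data are examined. No survey question, sample size or data collection changes.

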The secondary objective(s) are to understand the user's experience with the Mosie Kit and it's safety.	Secondary endpoints are: perceived ease of use and perceived safety.	The perceived ease of use is being examined as a secondary endpoint because being able to follow the instructions and use the kit as designed will directly affect whether the semen is deposited at or near the cervix having a direct effect on the results. Perceived ease of use is viewed as a mediating variable. Finally, perceived safety of the Mosie Kit will be examined. It is expected to be a moderating variable.	In order for the delivery of sperm at or near the cervix, the user needs to maximize the sperm drawn up into the Mosie syringe, insert it into the vagina, and deposit the sperm at or near the cervix. Because the Mosie syringe is inserted into the vagina, it is important to understand any perceived issues or concerns related to safety and use of the syringe.
Tertiary/Exploratory			
The tertiary objective will be to examine the pregnancy rate of people with different self-reported sources of infertility. Given the Pandemic, exploratory effect of COVID-19 on family planning, stress and pregnancy results will be examined.	Because the reason for a person's or couple's infertility might affect pregnancy rates, the reason for the infertility will also be examined. This will provide information as to whether the Mosie Kit is more effective given a specific source of infertility. The pandemic has caused an overall increase in stress, higher stress can affect fertility.	The source of infertility may play a mediating role in a successful pregnancy. For example, it might be more likely that a couple with a woman with no known infertility issue using Mosie might be more likely to get pregnant than a woman with a specific known infertility issue. Stress can play a mediating role in pregnancy. Concern over future stability and	Women who do not have a fertility issue might be more likely to get pregnant when the sperm is successfully deposited at or near the cervix. For example, this would help if the infertility was rooted in Erectile Dysfunction (ED). Stress hormones can affect pregnancy outcome. Stressful and uncertain times make people more

Page 14

planning may be family planning. expanding their families.
--

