9.1 Statistical Hypotheses and General Statistical Approach

The primary objective is to understand the outcome of using the Mosie kit for Intracervical insemination, i.e. pregnancy rate after its use. Specifically the hypothesis is as follows.

Primary hypothesis 1: Pregnancy rates using the at-home insemination Mosie Kit to deposit semen near or at the cervix (i.e. intracervical insemination) are equivalent or better than traditional in doctor's office intrauterine insemination (IUI). Conversely the null hypothesis is that the pregnancy rates using the at-home insemination Mosie Kit to deposit semen near or at the cervix do not have higher rates of pregnancy than in doctor's office IUI.

Analysis: Comparison of total rates of pregnancy using the Mosie Kit to the 10-20% rate reported for IUI by the American Pregnancy Association.

Primary Hypothesis 2: Pregnancy rates of LGBTQ couples or single women using the Mosie Kit where the female has no know fertility issues will be higher than that of heterosexual couples with a known fertility cause or those that are designated as having an unexplained fertility issue. The alternative hypothesis is that people with no known

fertility issues using the Mosie Kit will have less pregnancies than heterosexual couples with known fertility issues.

Analysis: Rate of pregnancy using the Mosie Kit will be obtained for the following groups: LGBTQ couples where carrying female has no known fertility issues, LGBTQ couples where carrying female has a known fertility issue, Heterosexual people with no known fertility issue, Heterosexual people with a known fertility issue, Single females with no known fertility issue and Single females with a known fertility issue. The rates of each group will be analyzed using descriptive statistics and the aggregate of the 3 groups with fertility issues will be compared with the aggregate of the 3 groups without fertility issues. An ANOVA will be used to compare the differences between groups.

Secondary Hypothesis 1: The participants perceived the Mosie Kit to be easy to use for its intended purpose. The alternative hypothesis is that the participants perceive the Mosie Kit to be difficult to use for its intended purpose.

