Analysis: Descriptive statistics will be used to analyze perceived safety. Qualitative analysis will be used on any comments made related to safety. Rates of vaginal infections will be analyzed using descriptive statistics.

Secondary Hypothesis 5: The majority of participants indicate they have little to no safety concerns related to using the Mosie Kit. Alternative hypothesis is the majority of participants will be very concerned or extremely concerned about the safety of using the Mosie Kit.

Analysis: Descriptive statistics of self-reported level of concern. Additionally, safety measures such as hand washing, disposing of the syringe after use, and reading the instructions will be examined using descriptive statistics.

Tertiary Hypothesis 1: There will be higher pregnancy rates when using the Mosie Kit when the source of infertility is male-based than when it is female-based. The alternative hypothesis is there will be lower pregnancy rates when using the Mosie Kit when the source of infertility is male-based than when it is female-based.

Analysis: In addition to the descriptive statistics a t-test will be run to examine this hypothesis.

Tertiary Hypothesis 2: There is a difference in pregnancy rates of people with known fertility issues depending on the source of their infertility. Specifically, the following sources of infertility will be examined if sufficient data is available.

- o PCOS
- Endometriosis
- Low AMH or low ovarian reserve
- Low sperm count
- Sperm motility issues
- Unexplained infertility
- Erectile dysfunction
- Performance issues or sexual anxiety, or inability to orgasm with partner.

Page 27

- Vaginismus or vulvodynia
- Tilted uterus
- Multiple uterus/cervix
- Loss of a fallopian tube

The alternative hypothesis is that there will be no difference in the fertility rates associated with different sources of infertility.

Analysis: Descriptive statistics, t-test, correlations and multiple ANOVAs will be used to examine this hypothesis.

Tertiary Hypothesis 3: There will be a difference between individuals who perform 2 insemination instances as described in the instructions and those that follow a different schedule or dosage number. The alternate hypothesis is that there will be no difference between the individuals that perform the minimum 2 insemination instances and those that follow difference dosage schedule.

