Appendix A: Online Survey Tool and Consent Form (Google Form)

This section shows what the Google Form will look like to the study participant. These are the questions the participant will be asked.

The first page of the study contains the consent form and the question that confirms the participant's agreement to participate.

There is skip logic for certain sections. For example, if the participant selects one cycle of using Mosie, the information related to cycles 2-6 will be skipped. If the participant selects that she is pregnant the questions related to the pregnancy will be asked, otherwise they will be skipped. If a donor was used, the questions related to producing a sperm sample will be skipped.

Note: Final language and questions might be tweaked or revised at any time to increase clarity.

MOSIE-001 © 2020 Mosie Baby Page 38

[figure not shown]
This is the inclusion/exclusion form.

If Participant selected to not participate in the study, he/she will see this screen next. If the participant said he/she is not 18 or older or has not used Mosie this screen will be displayed.

[figure not shown]

Qualifying participants will continue the survey on this page.

[figure not shown]

[figure not shown]
	ch of these diagnoses or issues do you believe are contributing to your rtility? *
	Not applicable
	PCOS
	Endometriosis
	Low AMH or low ovarian reserve
	Low Sperm count
	Sperm motility issues
	Erectile Dysfunction
	Performance issues or sexual anxiety, or inability to orgasm with partner
	Vaginismus or vulvodynia
	Tilted Uterus
	Multiple uterus/cervix
	Unexplained infertility
	Have only one functioning fallopian tube
П	Other:

[figure not shown]
No other method	is attempted			
Male/Female into	ercourse			
IVI or syringe oth	ner than Mosie			
IUI				
Femara				
Clomid				
IVF				
Cervical Cap				
Other:				
	None	1	2	3 or more
How many pregnancies have you had?	0	0	0	0
pregnancies	0	0	0	0
pregnancies have you had? How many live births have you had? How many pregnancies have you had that were	0	0	0	0
pregnancies have you had? How many live births have you had? How many pregnancies have you had	0	0	0	0

[figure not shown]

[figure not shown]
	0	1	2	3+
24-48 hours prior to ovulation	0	0	0	0
within 24 hours of ovulation	0	0	0	0
24-48 hours after ovulation	0	0	0	0
48+ hours after ovulation	0	0	0	0
Did you use Mosie fo Yes No	or another cy	cle?		

[figure not shown]

[figure not shown]

[figure not shown]

[figure not shown]

Mosie Kit Survey

* Required

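### The survey records semen source but no planned group comparison uses it, so Tertiary Hypotheses 1 and 2 (and, in part, Primary Hypothesis 2) are confounded by donor sperm, with unknown size and sign

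*Combined protocol and SAP*

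**What the plan says.** Tertiary Hypothesis 1 in Section 9.1 reads: "There will be higher pregnancy rates when using the Mosie Kit when the source of infertility is male-based than when it is female-based". Its analysis is: "In addition to the descriptive statistics a t-test will be run to examine this hypothesis". Tertiary Hypothesis 2 compares a list of diagnoses, including low sperm count and sperm motility issues, where data suffice: "Descriptive statistics, t-test, correlations and multiple ANOVAs will be used to examine this hypothesis". Section 3 gives the intended reading of pregnancy rate by infertility source: "This will provide information as to whether the Mosie Kit is more effective given a specific source of infertility".

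The survey in Appendix A expects donor use and records it. It asks what type of sample was used, with a legible option for frozen sperm-bank semen. A preparation checklist offers "Thawed out donor sperm from sperm bank", and the skip logic says: "If a donor was used, the questions related to producing a sperm sample will be skipped".

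No group comparison takes this up:
- Section 5.2 excludes only people who never used the kit.
- Section 9.4.2 lists age, sex, race/ethnicity, SES, relationship preference and male/female infertility issues as subgroup factors.
- Section 9.4.3 describes the exploratory model: "This will include the source of infertility, age, number of inseminations, number of cycles, lying time, and type of relationship".

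Primary Hypothesis 2 begins: "Pregnancy rates of LGBTQ couples or single women using the Mosie Kit where the female has no know fertility issues will be higher". The comparator is heterosexual couples with a known or unexplained fertility issue. The analysis forms six groups from relationship type and fertility issue, then compares the three groups with an issue, pooled, against the three without.

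**The concern.** The semen is what the kit delivers. When a couple reports low sperm count or poor motility and then uses donor sperm, the reported problem plays no part in that insemination. The plan still counts the outcome as evidence of how the kit performs in male-factor infertility. Any male-versus-female difference therefore mixes two things: the infertility source and whose semen was used.

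The result is meant to be acted on. Section 2.3.2 says the findings will help users decide whether the kit suits them, and Section 10.1.3 allows aggregate results in marketing. A couple with low sperm count who intend to use the partner's semen could be guided by a rate made up partly of donor-sperm pregnancies.

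Primary Hypothesis 2 has a related problem. Section 2.2 describes single and lesbian users as people with no male partner, and calls the husband's sperm the most popular source for insemination. As worded, the hypothesis contrasts groups that probably differ in semen source as well as in the woman's fertility status.

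**Working it through.** **Plan's own figure.** The only precision figure is for the whole sample (Section 9.2). 1.96 × √(0.25/500) = 4.4 points, as stated, and n = 384 gives 5.0 points. It reproduces, but it does not address comparisons between infertility groups.

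**Form of the bias, Tertiary Hypothesis 1.** Let d_M and d_F be the donor shares in the male- and female-factor arms. Let p_own be the own-semen pregnancy rate, equal in both arms (no true difference), and p_don the donor rate. Each arm's observed rate is (1 − d) × p_own + d × p_don, so

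bias = (d_M − d_F) × (p_don − p_own).

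**Inputs.**
- p_don: Section 2.2 cites a study of home insemination with 13 pregnancies among 29 women in six cycles. Its title in Section 11 says cryopreserved donor semen. 13/29 = 44.8%. As a check, the cited crossover study of single women using donor sperm gives 9% per ICI cycle; if constant, 1 − 0.91⁶ = 43% over six cycles.
- p_own: not given for kit users. 20% is an assumption. The range 10–35% borrows the six-cycle IUI range in Section 4.1.
- d_M, d_F: not given.

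**Scenario with p_own = 20% and d_F = 0** (bias = d_M × 0.248):

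| d_M | Bias |
|---|---|
| 10% | +2.5 points |
| 30% | +7.4 points |
| 50% | +12.4 points |

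**Chance of a false positive.** Section 9.4.1 makes directional tests one-tailed at 0.05. Assume 100 per arm, p_don = 45%, p_own = 20%, d_M = 20% and d_F = 0. The expected rates are 25% and 20%. The null SE is √(2 × 0.225 × 0.775/100) = 0.0591, and the SE at these rates is √((0.25 × 0.75 + 0.20 × 0.80)/100) = 0.0589. Then Φ((0.05 − 1.645 × 0.0591)/0.0589) = Φ(−0.80) = 21%, against 5% nominal. Over p_own = 10–35% and d_M = 5–50%, the bias runs from +0.5 to +17.5 points and the false-positive chance from 6% to 94%.

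**The sign can reverse.** There are two routes.
- Donor use may be greater in the female-factor arm. Section 4.2 classifies single and LGBTQ women with a known cause by infertility source, so donor users can fall there. With d_M = 10%, d_F = 30% and p_own = 20%, the bias is −0.20 × 0.248 = −5.0 points.
- Own-semen rates may be higher than donor rates. Section 2.2, discussing husband's sperm, cites 69%, 43% and 25% by age band in couples with vaginismus, erectile dysfunction or premature ejaculation. With d_M = 30% and d_F = 0, these give 0.3 × (0.448 − 0.69) = −7.3, 0.3 × (0.448 − 0.43) = +0.5 and 0.3 × (0.448 − 0.25) = +5.9 points.

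**Primary Hypothesis 2.** Assume donor use of 95% in LGBTQ/single users and 5% in heterosexual users. The contrast as worded carries 0.95 − 0.05 = 90% of any donor effect: 9 points for a 10-point effect. In the planned aggregate, a side with LGBTQ/single fraction x has donor share 0.05 + 0.90x.
- x = 0.80 without an issue and 0.30 with one: shares 0.77 and 0.32, difference 0.45, so 4.5 points.
- x = 0.40 on both sides: shares 0.41 and 0.41, difference 0, so no bias.

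**The case against.** **Sample type is not ignored altogether.** Section 9.4.1 promises descriptive statistics for every survey question, 9.1 plans further analysis of how people use the kit, and 9.4.3 includes relationship type, a proxy for donor use. This is true, but a tabulation does not separate donor users within a comparison. Nor does relationship type identify heterosexual couples who used a donor, who are the respondents at issue in Tertiary Hypotheses 1 and 2.

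**Primary Hypothesis 2.** A reader might infer that donor users sit on only one side of this comparison. That fits the hypothesis as worded but not the planned analysis. The three-versus-three aggregate has LGBTQ and single users on both sides, so the confounding is diluted and disappears only if the shares balance. The six separate rates already allow a comparison of issue with no issue among single women and among LGBTQ couples. Section 3 also names low sperm count and motility among its reasons for expecting a difference, so the protocol does not attribute the whole contrast to the woman's fertility. All of this stands and makes this part minor.

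**Feasibility and new bias.** The legible part of the sample-type item shows only the sperm-bank option, and another survey question groups partner and known donor together. Whether the two can be separated is therefore unverified. Restricting to partner semen conditions on a choice that may follow severity and could select milder male factor. Twelve diagnoses split by sample type within about 500 surveys will give small cells. These points stand and shape the remedy.

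**Importance.** These are tertiary, self-reported comparisons. That limits priority, but the remedy costs little.

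**Conclusion.** The point holds as confounding of unknown size and sign. Tertiary Hypotheses 1 and 2 compare infertility sources without regard to whose semen was used, although the survey asks about it and Section 3 reads the result as kit effectiveness by source. The argument is clearest for low sperm count and motility, where donor sperm bypasses the reported problem. It is weaker for erectile dysfunction and performance problems, where the partner's semen may be normal.

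A reader might infer that donor use inflates the male-factor rate in the direction Tertiary Hypothesis 1 predicts. The documents do not support that. It needs a higher donor share in the male-factor arm together with a donor rate above the own-semen rate (or both reversed), and the documents establish neither for kit users. The +2.5 to +12.4 points rest on one 29-woman arm, an assumed 20% own-semen rate and no donor use in the female-factor arm. They also use six-cycle rates, so shifts would be smaller for respondents with fewer cycles. They show that the effect could matter, not that it will occur.

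The change is worth making because it is inexpensive, not because a particular bias has been shown.

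**What to change.** 1. In 9.1, run Tertiary Hypothesis 1 (both arms) and the low-sperm-count and motility comparisons of Tertiary Hypothesis 2 (with their comparator groups) in partner-semen users, or stratified by sample type. Report donor-sperm users separately.
2. Show the unrestricted result alongside, because restriction may select milder male factor.
3. Report the Primary Hypothesis 2 group rates by sample type.
4. Add sample type to the subgroup list in 9.4.2 and the model in 9.4.3.
5. Before launch, confirm that the sample-type item separates partner from known-donor semen. Appendix A allows questions to be revised. The survey is anonymous with no follow-up (Section 4.3), so the distinction cannot be recovered later.

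The cost is wording in the analysis plan, possibly one survey response option, and smaller groups in the restricted or stratified comparisons. If the existing item already makes the distinction, no new data are needed.
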